3.3 Blinding Procedures

There are no blinding procedures to be followed, as study is open-label.

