7.3 Immunogenicity Assessment

The measures of immunogenicity used in this study are standard, i.e., widely used and generally recognized as reliable, accurate, and relevant (able to describe the quality and extent of the immune response). Testing will be conducted by a GSK or designated laboratory in a blinded manner towards the treatment arm and the visit.

The functional measure of immunogenicity used in this study, Serum Bactericidal Assay (SBA), is a measure of the ability of antibodies, mediated with complement, to kill meningococci, and is widely used and generally recognized as the serological correlate of protection. Human Serum Bactericidal Assay using human complement (hSBA) for *N.meningitidis* serogroups A, C, W, Y and serogroup B strains will be performed in GSK, Clinical Laboratory Sciences, Marburg (Germany) or in a qualified and certified laboratory designated by GSK using the identical standardized, validated procedures with adequate controls.

(Amended 4 April 2018)

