# 6. DETERMINATION OF PROTOCOL DEVIATIONS

#### **6.1** Definition of Protocol Deviations

CSR reportable PD are defined in accordance with ICH E3 as important PDs related to study inclusion or exclusion criteria, conduct of the trial, subject management or subject assessment resulting in the potential to jeopardize the safety or rights of the trial subjects or the scientific value of the trial.

All reportable PDs will be evaluated before the analysis and classified according to ICH into the following five categories:

- Subject developed withdrawal criteria during the study but was not withdrawn
- Underlying medical condition forbidden by the protocol or which may influence immune response (PD code 240).
- Subject had contraindication for a subsequent study vaccination but was vaccinated (PD code 220).
- Concomitant infection related to the vaccine which may influence immune response (PD code 250).
- Subject received wrong vaccine or incorrect dose
- Study vaccine was not administered at all (PD code 100)
- Vaccine administration not according to protocol (PD code 140.x).
- Randomization failure (vaccination not according to randomization) (PD code 120).
- Subject took an excluded concomitant medication
- Administration of concomitant vaccine(s) forbidden in the protocol (PD code 150.x).
- Administration of any medication forbidden by the protocol (PD code 230.x).
- Subject randomized and did not satisfy the entry criteria
- Subject did not meet entry criteria (PD code 200).
- Deviation from key study procedures
- Subject did not comply with study vaccination schedule (PD code 140.x).
- Subject did not provide any post-vaccination unsolicited safety data (PD code 115.x).

- Subject did not provide any post-vaccination solicited safety data (PD code 116.x).
- Subject did not comply with blood draw schedule (PD code 270.x).
- Serological results not available post-vaccination (PD code 110.x).
- Obvious incoherence, abnormal serology evolution or error in data (PD code 112).

CSR reportable PDs will lead to exclusion of the subject or part of the subject's data from at least one analysis set.

The number of subjects in any and by PD category will be summarized by vaccine, center and overall. Individual subject listings will be provided in an appendix, sorted by subject and by PD category.

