Prior to the analysis, designated GSK staff will develop a memo that describes the PDs that led to exclusions from analysis sets. This memo will be signed off by at least the Biostatistician and the Cluster Physician and will be included in the trial master file (Exclusion Memo).

Prematurely terminating study participation for reasons such as withdrawal of consent or occurrence of adverse events (including death) is not considered as a PD. The missing assessments that should have otherwise been collected for that subject later in the study are also not considered as a PD.

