## **6.2** Determination of Protocol Deviations

A set of listings will be provided to the Clinical Research and Development Lead (CRDL) and the Study Delivery Lead (SDL) for review according to SOP MON-11, on an ongoing basis during the study.

The listings will be programmed following the list presented in table in section 7.7, specifically using the PD codes specified in the first column.

After the review, the CRDL and the SDL will provide the Biostatistician with:

- An assessment of CSR reportable PDs based on blinded clinical data review.
- An assessment of subjects without PDs (e.g., premature withdrawals due to adverse event, withdrawal of consent) who should be excluded from an analysis set.

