110.d.502	Serology results are not available Serological results (A, C, W, Y and 4 B strains) are not available	Day 91			EXC (naive only)			EXC (naive only)
112.102	Obvious deviation from Laboratory Manual or error in laboratory data (HT-SBA)	Day 1				EXC		EXC
112.202	Obvious deviation from Laboratory Manual or error in laboratory data (HT-SBA)	Day 6 (follow on) Day 66 (naive)						EXC

PD code	PD Description	Study objective/ period	FAS IMM Persistence (Day 1)	FAS IMM (Day 31)	FAS IMM (Days 6, 31/Days 66,	PPS IMM Persistence (Day 1)	PPS IMM (Day 31)	PPS IMM (Days 6, 31/Days 66,
112.302	Obvious deviation from Laboratory Manual or error in laboratory data (HT-SBA)	Day 31			91)		EXC	EXC (follow on only)
112.502	Obvious deviation from Laboratory Manual or error in laboratory data (HT-SBA)	Day 91						EXC (naive only)
120.100	Randomization failure to treatment	Day 1				EXC (naive only)	EXC (naive only)	EXC (naive only)
140.100	Vaccination not according to protocol	Day 1				EXC	EXC	EXC
140.300	Vaccination not according to protocol	Day 61 (Naive only)						EXC (naive only)
150.100	Administration of forbidden vaccine	Day 1 (before BS_1)				EXC	EXC	EXC
150.300	Administration of forbidden vaccine	Day 1 (after BS_1)- day 7					EXC	EXC
150.500	Administration of forbidden vaccine	-7/+7 2 nd vaccination (naive only)						EXC (naive only)
200	Subject did not meet entry criteria	Day 1 – end of study				EXC	EXC	EXC

PD code	PD Description	Study objective/ period	FAS IMM Persistence (Day 1)	FAS IMM (Day 31)	FAS IMM (Days 6, 31/Days 66, 91)	PPS IMM Persistence (Day 1)	PPS IMM (Day 31)	PPS IMM (Days 6, 31/Days 66, 91)
220	Subject had contraindication for a subsequent study vaccination but was vaccinated	Day 1- Day 61 (naive only)						EXC
230.101	Administration of forbidden medication	Day 1				EXC	EXC	EXC
230.102	Administration of forbidden medication: ANTIBIOTICS	Day 1 (before BS_1)				EXC		
230.201	Administration of forbidden medication	Day 6 (follow on) Day 66 (naive)					EXC (follow on only)	EXC
230.202	Administration of forbidden medication: ANTIBIOTICS	Day 6 (follow on) Day 66 (naive)						EXC
230.301	Administration of forbidden medication	Day 31					EXC	EXC
230.302	Administration of forbidden medication: ANTIBIOTICS	Day 31 (before BS_2)					EXC	EXC (follow on only)
230.501	Administration of forbidden medication	Day 91						EXC (naive only)
230.502	Administration of forbidden medication: ANTIBIOTICS	Day 91						EXC (naive only)

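### SAP 6.1 defines PD code 112 more broadly than the SAP 7.7 table, so a subject's titre course could decide whether that subject stays in the PPS

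*SAP*

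**What the plan says.** SAP 6.1 sorts reportable deviations into five categories. Under departures from key study procedures it includes "Obvious incoherence, abnormal serology evolution or error in data (PD code 112"). Neither document defines incoherence or abnormal evolution or gives a threshold. The same section states that "CSR reportable PDs will lead to exclusion of the subject or part of the subject's data from at least one analysis set".

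The SAP 7.7 table describes codes 112.102, 112.202, 112.302 and 112.502 as "Obvious deviation from Laboratory Manual or error in laboratory data (HT-SBA"). It does not mention the pattern of titres.

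SAP 6.2 says of the deviation listings: "The listings will be programmed following the list presented in table in section 7.7, specifically using the PD codes specified in the first column". After reviewing them, the clinical and study delivery leads give the biostatistician "An assessment of CSR reportable PDs based on blinded clinical data review". On timing, SAP 6.1 says: "Prior to the analysis, designated GSK staff will develop a memo that describes the PDs that led to exclusions from analysis sets".

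On masking, Protocol 3.3 says: "There are no blinding procedures to be followed, as study is open-label". Protocol 7.3 has the assays run "in a blinded manner towards the treatment arm and the visit".

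**The concern.** One code has two meanings. Under 7.7 it needs something to have gone wrong with a sample, an assay or a record. Under 6.1 an unexpected series of titres is enough, with nothing else shown to be wrong.

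That matters because change in titre is itself an outcome. The secondary endpoints in Protocol 8.1.2.2 include the four-fold rise and the within-subject GMR from Day 1. A subject whose titre does not rise after the booster is a result; calling that course abnormal and removing the subject is selection on the endpoint. It also fits poorly with Protocol 8.3.8, which defines a deviation as a departure from study design or procedures.

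What is at stake is the PPS. It is run beside the FAS for every immunogenicity objective. If subjects can leave it because of their titres, it is a weaker check on the FAS.

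**Working it through.** **1. The two definitions side by side.**

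| | SAP 6.1 | SAP 7.7 table |
|---|---|---|
| Data or laboratory error | yes | yes |
| Laboratory Manual deviation | not named | yes |
| Incoherence | yes, undefined | no |
| Abnormal titre course | yes, undefined | no |

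**2. Which one governs.** Section 6.2 ties the listings to 7.7, which points to the narrower meaning, but no sentence says that 7.7 overrides 6.1. The sections differ elsewhere too: code 250 is in 6.1 but absent from the table, and non-compliance with the vaccination schedule is 140.x in 6.1 but 260.x in the table. A reader cannot assume that the two were reconciled.

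**3. Which analysis sets are touched (7.7 table).**
- 112.102 (Day 1): PPS Persistence and PPS Days 6, 31/66, 91.
- 112.202 (Day 6 or 66): PPS Days 6, 31/66, 91.
- 112.302 (Day 31): PPS Day 31 and, for follow-on subjects, PPS Days 6, 31/66, 91.
- 112.502 (Day 91, naive): PPS Days 6, 31/66, 91.
- No FAS column is marked for any of these codes.

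The FAS is the set named in Protocol 8.4.2.2.2 and 8.4.3.2.2 and in SAP 11.3.

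**4. Whether the safeguards remove the selection.**
- *Memo before analysis.* A titre course can be judged only once the titres are seen, so the exclusion depends on the outcome whenever the memo is signed.
- *Blinded review.* No masking method is described, and SAP 4.2 marks blinding as not applicable. Follow-on subjects are bled on Days 1, 6 and 31 and naive subjects on Days 1, 31, 66 and 91, so titres shown by visit distinguish the two. Even perfect masking of group would leave selection on titre.
- *Blinded assay.* This protects the measurement, not the later decision to exclude.

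**5. Illustrative size.** The plan states no figure to reproduce. Assumptions: 100 subjects per group (the follow-on target in Protocol Table 3.1-2); the response rates, GMRs and numbers excluded are mine.

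Four-fold rise, removing k non-responders from x responders in 100: rate = x/(100 − k).

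| Starting rate | k = 2 | k = 5 |
|---|---|---|
| 70% | 70/98 = 71.4% | 70/95 = 73.7% |
| 85% | 85/98 = 86.7% | 85/95 = 89.5% |
| 95% | 95/98 = 96.9% | 95/95 = 100% |

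For 85%, the Clopper-Pearson 95% interval moves from 76.5–91.4% to 81.5–94.8% with k = 5.

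Removing responders with an implausibly high rise goes the other way: rate = (x − k)/(100 − k). From 85% this gives 83/98 = 84.7% or 80/95 = 84.2%.

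GMR, removing k subjects whose titre fell four-fold: new GMR = 10^[(100·log10 G − k·log10 0.25)/(100 − k)].
- G = 10: 10.8 for k = 2 (+8%) and 12.1 for k = 5 (+21%).
- G = 4: 4.2 for k = 2 (+6%) and 4.6 for k = 5 (+16%).

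**The case against.** The strongest reply is that 6.1 is a general list that 7.7 refines. Listings are programmed from 7.7, and code 112 sits in 6.1 under procedural departures, so the narrow meaning is probably the one intended. That is a fair reading and it lowers the likelihood of harm. It does not settle the matter, because 6.1 still names titre evolution as a ground and the SAP gives no order of precedence.

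The safeguards also count for something. A review described as blinded, a memo signed by at least the biostatistician and the cluster physician, and individual listings all make group-driven exclusion harder and more visible. However, the planned summary counts deviations by category, and code 112 shares its category with missing safety data, blood-draw timing and missing serology. Its own count would not show there.

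The effect could run in either direction, and the illustration assumes that all excluded subjects are of one kind. That stands: the figures show what the wording permits, not what is expected.

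Finally, incoherent serial titres can be the only sign of a swapped or mislabelled sample, and a laboratory blinded to visit cannot by itself detect a swap between visits. This also stands, and it shapes the fix.

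**Conclusion.** The two definitions of code 112 conflict, and the one in 6.1 permits exclusion from the PPS on the basis of titre course. This should be corrected, but its reach is limited to the PPS and its value as a check on the FAS.

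Three stronger readings are not supported:
- *A reader might infer that the main results are exposed.* They are not. Code 112 excludes from no FAS set, the FAS is the named set, and there are no hypotheses or success criteria.
- *A reader might infer that the exclusion selects directly on the primary endpoint.* The primary endpoints are the percentage at or above LLOQ and the GMT at Day 1 alone, which are levels and not courses. Code 112.102 does reach PPS Persistence, but the direct overlap is with the secondary four-fold-rise and GMR endpoints.
- *A reader might infer from the open label that exclusions will be decided with knowledge of group.* SAP 6.2 calls the review blinded. The gap is that it does not explain how, and that masking group would not remove selection on titre.

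The textual conflict needs no assumption. That only the PPS is affected rests on the 7.7 mapping being applied. The documents do not determine the size; the figures above depend on assumed rates and assumed exclusions.

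**What to change.** In SAP 6.1, replace the description of code 112 with the 7.7 wording, dropping incoherence and abnormal evolution as grounds in themselves. Add that an incoherent or unusual titre series may trigger a check of sample identity, handling and assay records, made without regard to vaccine group. Because the laboratory is blinded to visit, the check must draw on sample-identity records as well as bench records. Exclude under code 112 only if a laboratory, labelling or data error is documented; otherwise the subject stays in the PPS. Report the number excluded under code 112 by vaccine group.

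The cost is a small wording change, one added count, and a record check when a series looks odd. The downside is that a sample error that cannot be documented may stay in the PPS.

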## **6.2** Determination of Protocol Deviations

A set of listings will be provided to the Clinical Research and Development Lead (CRDL) and the Study Delivery Lead (SDL) for review according to SOP MON-11, on an ongoing basis during the study.

The listings will be programmed following the list presented in table in section 7.7, specifically using the PD codes specified in the first column.

After the review, the CRDL and the SDL will provide the Biostatistician with:

- An assessment of CSR reportable PDs based on blinded clinical data review.
- An assessment of subjects without PDs (e.g., premature withdrawals due to adverse event, withdrawal of consent) who should be excluded from an analysis set.

# 6.3 Exclusions of Individual Values for Safety Analysis

Some local and systemic adverse events will be directly measured by the subject and will not be subject to a reconciliation process, even if they are biologically implausible. Therefore these implausible measurements will be removed from the analysis but included in listings. Implausible measurements are summarized in the table below:

**Table 6.3-1:** Implausible Solicited Adverse Events

Parameter	Implausible measurements
Body temperature	≤ 33°C or ≥ 42°C
Erythema	For subjects ≥ 6 years: ≥ 900 mm
	Measurements < 0 mm
Induration	For subjects $\geq$ 6 years: $\geq$ 500 mm
	Measurements < 0 mm

# 7. ANALYSIS SETS

#### 7.1 All Enrolled Set

All screened subjects who provide informed consent and provide demographic and/or other baseline screening measurements, regardless of the subject's randomization and vaccination status in the trial, and receive a subject ID.

Demography and baseline characteristics tables as well as subject listings will be produced on the All Enrolled Set.

# 7.2 Exposed Set

All subjects in the All Enrolled Set who receive a study vaccination.

# 7.3 Full Analysis Set (FAS), Immunogenicity Set

Full Analysis Set Persistence (24 months after last vaccination in V102\_15) – FAS Persistence (Day 1)

All subjects in the All Enrolled Set, who are randomized (if naive), and

• Provide evaluable serum sample with results for at least one serogroup B test strain or serogroups A, C, W or Y at Day 1 in the extension study.

Full Analysis Set Immunogenicity (Day 31, after booster dose [follow-on]/first dose [naive]) – FAS Immunogenicity (Day 31)

All subjects in the All Enrolled Set, who are randomized (if naive), and:

- Receive at least one study vaccination and,
- Provide evaluable serum sample with results for at least one serogroup B test strain or serogroups A, C, W or Y (only after MenABCWY vaccination) at Day 31 in the extension study.

Full Analysis Set Immunogenicity (Days 6 and 31, after booster dose [follow-on]/ Days 66 and 91 after second dose [naive]) – FAS Immunogenicity (Days 6, 31/Days 66, 91)

All subjects in the All Enrolled Set, who are randomized (if naive), and:

- Receive at least one study vaccination and,
- Provide evaluable serum sample with results for at least one serogroup B test strain or serogroups A, C, W or Y (only after MenABCWY vaccination) at Day 1,

and in addition at least at Day 6 or Day 31 (follow-on subjects) / Day 66 or Day 91 (naive subjects) in the extension study.

In case of vaccination error, subjects in the FAS sets will be analyzed "as randomized" (i.e., according to the vaccine a subject was designated to receive, which may be different from the vaccine the subject actually received).

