# All subjects in the PPS Persistence who:

• Provide evaluable serum sample with results for at least one serogroup B test strain or serogroups A, C, W or Y (only after MenABCWY vaccination) at each visit on Day 1, Day 6 and Day 31 (follow-on subjects) / Day 1, Day 66 and Day 91 (naive subjects) in the extension study.

PPS are subsets of FAS and should be always defined even if the objectives do not require it.

\_

<sup>5 Booster dose (follow-on) and first dose (naive in secondary objectives 2 and 4) / first and second dose (naive in secondary objectives 3 and 5).

Subjects might be excluded due to other reasons than protocol deviations (e.g., subjects who withdrew informed consent).

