# 7.7 Overview of Analysis Sets by PD Code

Table 7.7-1: Safety Sets

PD code	PD Description	Study Objective/ Period	All Exposed Set	Overall Safety Set	Safety Set, Solicited AEs, Period 1, T6H-D7	Safety Set, Solicited AEs, Period 2, T6H-D7	Unsolicited Safety set
	Exclusion code		EXPFL	SAFFL	SSS10FL	SSS11FL	SSU10FL
100	Study vaccine not administered AT ALL	All Study	EXC	EXC	EXC	EXC	EXC
115	Subject did not provide any post-vaccination unsolicited safety data	All Study					EXC
116.1	Subject did not provide any post-vaccination solicited safety data after vaccination 1	All Study (follow on)/First vaccination (Naive)			EXC		
116.2	Subject did not provide any post-vaccination solicited safety data after vaccination 2*	Second vaccination				EXC	

EXC = excluded from this analysis set.

\*applicable to naive subjects only.

PD code	PD Description	Study objective/ period	FAS IMM Persistence (Day 1)	FAS IMM (Day 31)	FAS IMM (Days 6, 31/Days 66, 91)	PPS IMM Persistence (Day 1)	PPS IMM (Day 31)	PPS IMM (Days 6, 31/Days 66, 91)
	Exclusion code		FAS10FL	FAS11FL	FAS12FL	PPS10FL	PPS11FL	PPS12FL
100	Study vaccine not administered AT ALL	Day 1 – End of study		EXC	EXC		EXC	EXC
110. 100	Serological results (A, C, W, Y and 4 B strains) are not available  Visit not done, blood draw not done	Day 1	EXC		EXC	EXC		EXC
110.d.102	Serology results are not available  Serological results (A, C, W, Y and 4 B strains) are not available	Day 1	EXC		EXC	EXC		EXC
110. 200	Serological results (A, C, W, Y and 4 B strains) are not available  Visit not done, blood draw not done	Day 6 (follow on) Day 66 (naive)			EXC			EXC
110.d.202	Serology results are not available  Serological results (A, C, W, Y and 4 B strains) are not available	Day 6 (follow on) Day 66 (naive)			EXC			EXC

	lential	

PD code	PD Description	Study objective/ period	FAS IMM Persistence (Day 1)	FAS IMM (Day 31)	FAS IMM (Days 6, 31/Days 66, 91)	PPS IMM Persistence (Day 1)	PPS IMM (Day 31)	PPS IMM (Days 6, 31/Days 66, 91)
110. 300	Serological results (A, C, W, Y and 4 B strains) are not available  Visit not done, blood draw not done	Day 31		EXC	EXC (follow on only)		EXC	EXC (follow on only)
110.d.302	Serology results are not available  Serological results (A, C, W, Y and 4 B strains) are not available	Day 31		EXC	EXC (follow on only)		EXC	EXC (follow on only)
110. 500	Serological results (A, C, W, Y and 4 B strains) are not available  Visit not done, blood draw not done	Day 91			EXC (naive only)			EXC (naive only)

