240	Underlying medical condition forbidden by the protocol	Day 1- end of study				EXC	EXC	EXC

$\sim$	~		
Con	†10	en:	tıa.
COL		$\iota\iota\iota\iota\iota$	ши.

PD code	PD Description	Study objective/ period	FAS IMM Persistence (Day 1)	FAS IMM (Day 31)	FAS IMM (Days 6, 31/Days 66, 91)	PPS IMM Persistence (Day 1)	PPS IMM (Day 31)	PPS IMM (Days 6, 31/Days 66, 91)
260.100	Did not comply with study vaccination schedule	Day 1					EXC	EXC
260.200	Did not comply with study vaccination schedule	Day 61 (naive only)						EXC
270.100	Did not comply with blood draw schedule*	Day 1				EXC		EXC
270.200	Did not comply with blood draw schedule	Day 6 (follow on) Day 66 (naive)						EXC
270.300	Did not comply with blood draw schedule*	Day 31					EXC	EXC (follow on only)
270.400	Did not comply with blood draw schedule	Day 91						EXC (naive only)

\*e.g. BD after vaccination

FAS = Full Analysis Set; PPS=Per Protocol Set; EXC = excluded from this analysis set.

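### The SAP section 7.7 exclusion table applies the per-protocol sample rule to FAS Immunogenicity (Days 6, 31/Days 66, 91), contradicting SAP 7.3 and Protocol 8.3.4

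*SAP*

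**What the plan says.** **FAS definition.** For FAS Immunogenicity (Days 6, 31/Days 66, 91), SAP 7.3 requires at least one study vaccination and an evaluable result at Day 1, "and in addition at least at Day 6 or Day 31 (follow-on subjects) / Day 66 or Day 91 (naive subjects"). Protocol 8.3.4 has the same rule.

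**PPS definition.** The corresponding per-protocol set in SAP 7.4 needs results "at each visit on Day 1, Day 6 and Day 31 (follow-on subjects) / Day 1, Day 66 and Day 91 (naive subjects"). Protocol 8.3.5 also requires all three samples.

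**Exclusion table.** The immunogenicity table in SAP 7.7 assigns exclusions by protocol-deviation code. FAS12FL is the flag for this FAS and PPS12FL the flag for the matching PPS. For missing serology, the FAS12FL column reads:

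- 110.100 and 110.d.102, Day 1: excluded.
- 110.200 and 110.d.202, period "Day 6 (follow on) Day 66 (naive"): excluded.
- 110.300 and 110.d.302, Day 31: "EXC (follow on only").
- 110.500 and 110.d.502, Day 91: "EXC (naive only").

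The legend states "EXC = excluded from this analysis set".

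**Use.** SAP 11.3 and Protocol 8.4.3.2.2 name the FAS as the analysis set for all secondary immunogenicity objectives, with the PPS analysed as well.

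**The concern.** The definition needs one of two post-dose results; the table removes a subject when either is missing. No row is conditional on the other post-dose sample also being absent, so the table gives the FAS the sample-availability rule that the text reserves for the PPS.

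If FAS12FL is programmed from the table, the FAS results for secondary objectives 2 and 4 lose subjects whom the protocol includes. The FAS and PPS then share one sample rule, so a comparison of the two carries no information about the effect of a missed draw. If FAS12FL is programmed from the text, the SAP misstates its own exclusions. Either way, two programmers could each follow the SAP and produce different analysis sets.

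**Working it through.** **1. Compare the rules pattern by pattern.** Let P1 be the first post-dose sample (Day 6 follow-on, Day 66 naive) and P2 the second (Day 31 follow-on, Day 91 naive).

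- FAS text: Day 1 and (P1 or P2).
- FAS12FL as printed: out if Day 1, P1 or P2 is coded missing.
- PPS text, samples only: Day 1 and P1 and P2.

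| Day 1 | P1 | P2 | FAS text | FAS12FL | PPS sample rule |
|---|---|---|---|---|---|
| yes | yes | yes | in | in | in |
| yes | yes | no | **in** | **out** | out |
| yes | no | yes | **in** | **out** | out |
| yes | no | no | out | out | out |
| no | any (4 patterns) | | out | out | out |

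Text and table agree in 6 of 8 patterns. FAS12FL matches the PPS sample rule in 8 of 8. The Day 1 exclusions are consistent with the text.

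**2. Can a partial exclusion reconcile them?** SAP 6.1 says "CSR reportable PDs will lead to exclusion of the subject or part of the subject's data from at least one analysis set". A 110.x code means that no serology result exists at that visit, so there is no visit value to remove. FAS12FL is a single flag covering both visits, and the legend defines the entry as exclusion from the set.

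**3. Who is coded?** On samples missing after premature termination, SAP 6.1 says: "The missing assessments that should have otherwise been collected for that subject later in the study are also not considered as a PD". Early terminators may therefore carry no 110.x code. Read literally, the table could drop a subject who stayed in the study and missed one draw, yet keep an early terminator with the same results.

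**4. Illustrate the size.** Assumptions: 100 subjects per group (the target in the schedule tables of both documents), missing rate m at each of three visits, every missing sample coded, Day 1 independent of the later visits, and correlation ρ between missingness at P1 and P2.

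- P(both missing) = m² + ρm(1−m)
- P(exactly one missing) = 2m(1−m)(1−ρ)
- Kept by text = 100(1−m)(1 − P(both))
- Kept by table = 100(1−m)(1 − P(both) − P(one))
- Single-visit n under the text (Day 1 plus that visit) = 100(1−m)²
- CI width ratio = √(single-visit n under the text / n kept by the table)

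For m = 5%, ρ = 0:

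- Text: 95 × (1 − 0.0025) = 94.76
- Table: 95 × 0.95² = 85.74
- Gap: 9.0 subjects
- Single-visit n: 90.25; √(90.25/85.74) = 1.026

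For m = 5%, ρ = 0.5:

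- P(both) = 0.0025 + 0.02375 = 0.02625; P(one) = 0.0475
- Gap: 95 × 0.0475 = 4.5 subjects
- Table: 95 × (1 − 0.07375) = 87.99; √(90.25/87.99) = 1.013

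| m | Text, ρ=0 | Table, ρ=0 | Gap, ρ=0 | Gap, ρ=0.5 | CI widening, ρ=0 | CI widening, ρ=0.5 |
|---|---|---|---|---|---|---|
| 2% | 98.0 | 94.1 | 3.8 | 1.9 | 1.0% | 0.5% |
| 5% | 94.8 | 85.7 | 9.0 | 4.5 | 2.6% | 1.3% |
| 10% | 89.1 | 72.9 | 16.2 | 8.1 | 5.4% | 2.6% |

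Gaps are computed before rounding.

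**The case against.** The strongest reply is that the harm depends on a derivation the reader cannot see. SAP 6.2 ties the deviation listings to the 7.7 table but does not say that the analysis-set flags are computed from it; the definitions sit in 7.3, and programming specifications are held elsewhere. There are also safeguards: a signed exclusion memo before analysis (SAP 6.1) and review of the exclusion file by a second programmer (SAP 16). This lowers the chance of an unnoticed error, but none of it says which rule is correct, and a reviewer could validate either.

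The illustration can also be called high. It treats every missing sample as coded, which early terminators may not be, and correlated missingness halves the gap. The only planning figure, at most 5% of subjects without serology, survives solely in sample-size text deleted by the amendment, so it does not bind; a 10% rate per visit lies well above it. These points stand as limits on size.

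Finally, the FAS and PPS would differ for other reasons in any case, because PPS12FL has further exclusions (for example codes 112, 140, 200 and 270). So the text rule would not isolate the effect of a missed visit either. That is fair, but under the table rule sample availability contributes nothing at all to the difference.

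**Conclusion.** The contradiction is real and sits in the current text of both documents. FAS12FL as printed excludes subjects with Day 1 and one post-dose result, whom SAP 7.3 and Protocol 8.3.4 include. It should be fixed before the exclusion file is programmed.

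The reach is limited. It concerns the descriptive secondary objectives 2 and 4. The primary objective (FAS10FL) and secondary objectives 1 and 3 (FAS11FL) are untouched, and a follow-on subject missing only Day 6 still contributes Day 31 there. A naive subject missing only Day 31 is not affected in FAS12FL. No hypothesis or success criterion depends on this set. Under the SAP's assumption that immunogenicity data are missing completely at random (SAP 8.2.2), the cost is precision and not bias: for missing rates of 2% to 10% per visit, about 2 to 16 subjects per 100, and single-visit intervals about 0.5% to 5.4% wider, across the two correlations shown. Those rates are assumptions, not figures from the plan.

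**What to change.** In the FAS12FL column of the SAP 7.7 immunogenicity table:

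- Keep the exclusions for code 100 and for a missing Day 1 result (110.100, 110.d.102).
- For follow-on subjects, otherwise exclude only when (110.200 or 110.d.202) **and** (110.300 or 110.d.302) apply.
- For naive subjects, otherwise exclude only when (110.200 or 110.d.202) **and** (110.500 or 110.d.502) apply.
- Leave the single-visit exclusions in PPS12FL only.

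Add a sentence that the section 7.3 definition governs the flag, including for early terminators who receive no 110.x code. With this change the table agrees with the text in all eight sample patterns.

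The cost is one SAP table correction and a check of one flag derivation. No new data are needed.
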